1.0 Objectives / Specific Aims

- Objective: Determine the optimal dose of IV N-acetylcysteine (NAC) to produce opioid reduction following spine surgery and estimate the difference in opioid consumption between placebo and the selected optimal dose.
- The primary outcome will be 12-hour postoperative opioid consumption.
- The secondary outcomes will be 6-hour postoperative opioid consumption.
- Other exploratory outcomes will include intraoperative opioid consumption, postoperative anesthesia care unit (PACU) opioid consumption cumulative, non-opioid analgesic administration, postoperative opioid consumption at additional time points, and VAS pain scores. Patient demographic data, surgical data (procedure, operative duration), preoperative opioid consumption, time to hospital discharge will also be collected.

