6.0 Number of Subjects

Sample size: 70 subjects

First 20 subjects: We will initially randomize 5 patients to each dose group (placebo, 50, 100, and 150 mg/kg) to estimate the dose response curve and to identify the optimal dose. After enrollment of the first 20 patients, the study will undergo review by the study team and statistician.

- If the dose response curve is adequate and the optimal dose identified, 15 additional patients will be randomized to placebo and 15 to the optimal dose to estimate the difference in opioid consumption between patients on placebo vs. the optimal dose. (Total of 50 subjects with 20 from dose response curve and 30 to estimate the difference in opioid consumption.)
- If the dose response curve is not adequate after the initial 20 subjects 5 per each dose group, we will randomize and enroll an additional 5 patients to each dose group (placebo, 50, 100, and 150 mg/kg) to estimate the dose response curve and to identify the optimal dose. Once the optimal dose is identified with these initial 40 patients, 10 additional patients will be randomized to placebo and 10 to the optimal dose to estimate the difference in opioid consumption between patients on placebo vs. the optimal dose. (60 patients total with 40 to create the dose response curve and 20 more to estimate the difference in opioid consumption.)
- A sample size of 20 subjects per group (placebo and optimal dose) allows us to estimate a 95% confidence interval for the mean difference in opioid consumption with a width of ± 0.64 standard deviations from the mean. We will plan to consent 70 subjects to account for withdrawal but will complete the study once 50 or 60 subjects (based on the number of subjects required to create the dose response curve) have completed the protocol.

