Patient and procedural characteristic will be recorded throughout the perioperative period. Demographic data (age, gender, race, weight, height, body mass index) and preoperative opioid consumption will be collected after completion of informed consent (yes or no; and consumption quantified if applicable). Surgical data (operative procedure and surgical duration) will be collected after surgery. Time of hospital discharge will be collected after the patient is discharged from the hospital.

Other exploratory outcomes will be collected as long as the patient is still in the hospital and able to self-report up to 48 hours post-operatively. Data will be collected from subject self-reporting their VAS score and using the electronic medical record. These data include intraoperative opioid consumption, postoperative anesthesia care unit (PACU) opioid consumption cumulative, non-opioid analgesic administration, postoperative opioid consumption up to 48 hours or discharge. VAS pain scores will be recorded pre-operatively, post operatively and at 24 hours unless discharged prior to 24 hours post operatively.

In order to identify the optimal IV NAC dose for perioperative opioid reduction and estimate the difference in opioid consumption between placebo and the selected optimal dose, the study will progress in two phases.

- In the first phase (20 subjects), we will attempt to identify the optimal dose. The optimal dose is defined as the dose or doses of NAC for which a $\geq 20\%$ reduction in opioid consumption relative to placebo is expected based on the dose response curve. If 20% reduction is not achieved, the optimal dose will be the maximum dose (150 mg/kg) administered during the study.
- In the second phase, after finding the optimal dose, 15 additional patients will be randomized to placebo and 15 to the optimal dose to estimate the difference in opioid consumption between patients on placebo vs. the optimal dose (30 subjects). A sample size of 20 subjects per group (5 from phase 1 and 15 from phase 2) allows us to estimate a 95% confidence interval for the mean difference in opioid consumption with a width of ± 0.64 standard deviations from the mean.
- If we are unable to create a dose response curve following the enrollment of the first 20 subject, an additional 20 subjects (5 per group) will be enrolled to create the dose response curve prior to starting the second phase.

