A pilot trial to determine the effective dose of N-acetylcysteine for opioid reduction in patients undergoing spine surgery.

NCT04562597

Statistical Analysis Plan Date: June 1, 2020

A pilot trial to determine the effective dose of N-acetylcysteine for opioid reduction in patients undergoing spine surgery.

Statistical Analysis Plan

An *a priori* sample size calculation was conducted to determine the precision of the estimated mean difference in opioid consumption at 12-hours between treatment groups in phase 2 for a fixed sample size. A sample size of 20 subjects per group was needed to estimate a 95% confidence interval for the mean difference in opioid consumption with a width of + 0.64 standard deviations from the mean.

The primary outcome of interest in phase 2 was opioid consumption at 12-hours postoperative. Additional opioid outcomes included opioid consumption over time (every 6 hours postoperatively up to 48 hours) and difference in opioid consumption between groups. Mean differences between treatment groups in opioid consumption at different postoperative times, including the primary outcome of 12 hours postoperative, were estimated from a linear mixed model including fixed effects for group, postoperative time, and their interaction and a random patient effect to account for correlation between measures collected on patients over time.

Descriptive statistics were calculated for patient and procedural characteristics across all treatment groups in phases 1 and 2. Additional phase 2 outcomes included time to first PACU opioid rescue dose, PACU VAS pain score, postoperative NRS pain scores, PACU duration, and time to hospital discharge.

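### The 'optimal dose' label is set once from a phase 1 point estimate, and nothing in the SAP ties the final data back to it

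*Protocol*

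**What the plan says.** Protocol section 1.0 opens the objective with "Determine the optimal dose of IV N-acetylcysteine (NAC) to produce opioid reduction following spine surgery"; the second half is to estimate the difference between placebo and the dose selected.

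Section 6.0 describes the start: "We will initially randomize 5 patients to each dose group (placebo, 50, 100, and 150 mg/kg) to estimate the dose response curve". If the curve is judged inadequate, section 10.0 provides that "an additional 20 subjects (5 per group) will be enrolled to create the dose response curve prior to starting the second phase", which makes 10 per dose and 40 patients.

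The selection rule is in section 10.0: "In the first phase (20 subjects), we will attempt to identify the optimal dose". A dose qualifies if at least a 20% "reduction in opioid consumption relative to placebo is expected based on the dose response curve". If 20% is not reached, 150 mg/kg is called optimal by default. The rule carries no interval and no required degree of certainty.

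Phase 2 follows: "If the dose response curve is adequate and the optimal dose identified, 15 additional patients will be randomized to placebo", and 15 to the selected dose (10 and 10 on the extended path). Section 10.0 counts 5 phase 1 and 15 phase 2 patients in each of the two final groups.

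The SAP says "The primary outcome of interest in phase 2 was opioid consumption at 12-hours postoperative". It estimates mean differences between groups from a linear mixed model with group, time and group-by-time terms and a patient random effect. Its only explicit mention of phase 1 concerns descriptive statistics for patient and procedural characteristics.

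**The concern.** One half of the objective has no written final analysis. The dose is named at the end of phase 1 from a point estimate, and no later step asks whether the completed trial still supports the name. The final comparison may show the selected dose falling well short of a 20% reduction, or the default may have been used because no dose reached 20%. In either case the plan as written still leaves that dose labelled optimal.

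A later trial would probably take its dose from this pilot. Its designers would see a label and a mean difference, but no estimated curve with uncertainty and no percent reduction to hold against the protocol's own criterion.

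**Working it through.** **Inputs.** From Protocol sections 6.0 and 10.0: 5 per dose, or 10 if extended; phase 2 adds 15 + 15 or 10 + 10; the threshold is 20%. The documents give neither an SD nor a curve shape. I assume a coefficient of variation (CV) of 0.6 to 1.0 and a straight line, with doses coded 0, 1, 2, 3. Standard errors (SE) are in SD units.

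**1. The plan's own figure.** Half-width with 20 per group = t(0.975, 38) × √(2/20) = 2.024 × 0.316 = 0.640. The stated 0.64 SD reproduces. The same formula gives 2.306 × 0.632 = 1.46 SD at 5 per arm and 2.101 × 0.447 = 0.94 SD at 10 per arm.

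**2. How often an inactive drug meets the 20% rule.** A straight line reaches 20% at some studied dose only if it does so at 150 mg/kg, that is, if 0.2a + 3b ≤ 0 for intercept a and slope b. Since a = (overall mean) − 1.5b, this quantity equals 0.2 × (overall mean) + 2.7b. With no effect its expectation is 0.2/CV.
- 5 per dose: variance = 0.04/20 + 7.29/25 = 0.2936, SD 0.542. At CV 0.6, 0.8 and 1.0, z = 0.333/0.542 = 0.615, 0.25/0.542 = 0.461 and 0.2/0.542 = 0.369. The probabilities are 27%, 32% and 36%.
- 10 per dose: variance = 0.04/40 + 7.29/50 = 0.1468, SD 0.383. Then z = 0.870, 0.653 and 0.522, giving 19%, 26% and 30%.

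Simulation with gamma data agrees with these figures. Each path was taken on its own, because the documents do not define an adequate curve.

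**3. Conflict with the final data.** This was simulated on the 50-patient path with no effect, CV 0.4 to 1.0, and the lowest dose reaching 20% carried forward (my reading, since the protocol allows more than one dose). Among trials that met the rule in phase 1, the final 20 vs 20 estimate was below 20% in about two thirds (CV 1.0) to nine tenths (CV 0.4).

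**4. What a final refit with a phase term adds (50-patient path).**
- Selected dose, separate means: √(1/20 + 1/20) = 0.316. The planned comparison already achieves this.
- Unselected dose, separate means: the dose itself keeps variance 1/5. The placebo level has variance 1/10 + (1/4)(1/10) = 0.125. So SE = √(0.2 + 0.125) = 0.570, against √(1/5 + 1/5) = 0.632 from phase 1 alone.
- Straight line, effect at 150 mg/kg: phase 1 alone gives 3/√25 = 0.60. Phase 2 adds 67.5, 30 or 7.5 to the within-phase sum of squares if 150, 100 or 50 mg/kg is carried forward. The SE becomes 3/√92.5 = 0.31, 3/√55 = 0.40 or 3/√32.5 = 0.53.

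**5. Bias of a pooled fit.** In the null trials that met the rule, the pooled 20 vs 20 estimate overstated the reduction by about 6 to 7 percentage points on the 50-patient path and 13 to 14 on the 60-patient path.

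**The case against.** Using one stage to select and a second to estimate is a coherent pilot design, and the trial calls itself a pilot. Much of this defence stands, and it rules out several stronger readings.

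- A reader might infer that the selected dose is never re-estimated or has no interval. Sections 6.0 and 10.0 plan a 95% confidence interval with 20 per group, and the SAP estimates the mean difference.
- A reader might infer that most of the data are ignored. The share of patients outside the dose choice is 30/50 = 60% on one path but 20/60 = 33% on the other, and all of them enter the primary comparison.
- A reader might say that the dose always rests on 5 per group. Section 6.0 plans otherwise: "If the dose response curve is not adequate after the initial 20 subjects 5 per each dose group, we will randomize and enroll" 5 more to each dose group.
- A reader might credit a refit with cutting the selected dose's SE from 0.63 to 0.32 SD. That gain belongs to the existing plan.
- Raw arm means would give higher false-selection rates, 49–62% at 5 per group, but the protocol's rule is based on the curve.

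It is also true that phase 2 adds nobody on the unselected doses, so a refit does little to rank them unless a parametric curve is assumed. What the defence does not supply is a dose-response model in the SAP, an interval for the unselected doses, a result on the percent scale, or any rule linking the final result to the label.

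**Conclusion.** The point holds in limited form and is a cheap improvement. The optimal-dose conclusion is fixed by a phase 1 point estimate, or by default, and no planned analysis revisits it. If the drug is inactive, the 20% rule is met in about 27–36% of trials at 5 per dose and 19–30% at 10. Among such trials on the 50-patient path, the final estimate usually falls below 20%.

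These rates rest on an assumed CV of 0.6 to 1.0 (0.4 to 1.0 for the conflict figure) and a straight line; the conflict figure also assumes that the lowest qualifying dose goes forward. The absence of a dose-response model and of a linking rule rests on the documents alone.

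The benefit of the change lies in what the conclusion is based on. Precision for the selected dose hardly changes. For an unselected dose the SE falls only from 0.63 to 0.57 SD with separate means; under a straight line the gain at 150 mg/kg depends on which dose was carried forward.

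**What to change.** Add one paragraph to the SAP:

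1. Name the dose-response model, and state that the phase 1 fit serves only to choose the phase 2 arm.
2. At the end, refit that model to all 50 or 60 patients with a term for phase. Report the estimated percent reduction with a 95% confidence interval at each studied dose.
3. Show beside it the phase 1 fit and a phase-2-only estimate for the selected dose.
4. State the dose conclusion from these final results. If they do not support the protocol's own 20% criterion, including when the default was used, report the arm as the dose carried forward and not as optimal.

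The cost is a paragraph and a model fit, with no extra patients or visits and no change to dosing or conduct. There are three limits. The pooled fit keeps the selection bias from phase 1, which is why the phase-2-only estimate is needed; its SE is √(2/15) = 0.37 SD or √(2/10) = 0.45 SD, against 0.32 pooled. The final fit may not favour the dose carried forward. And the change does not lower the chance of a false selection in phase 1; it only stops that selection from standing as the final answer unchecked.

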11.0 Data Management

Research data will be coded. Upon enrollment, subjects will be assigned a randomized numerical identifier for the remainder of the study. This number will be used to label research charts and paperwork associated with the subject. An electronic enrollment log will link patient name and MRN with his/her study ID number. This log will be kept separate from all research data. All paper information will be kept in a locked cabinet in a locked office. All electronic data will be kept on MUSC's password protected server.

Electronic data will be kept on a password protected MUSC server and a redcap database. All paper documents will be kept in a locked cabinet, in a locked office. Only IRB approved, CITI trained study team members will have access to the data. All data will be kept for 6 years per MUSC policy.

13.0 Provisions to Monitor the Data to Ensure the Safety of Subjects (if applicable)

Any adverse events related to NAC will be treated according to MUSC Hospital policy and procedures and the practice of the Department of Anesthesia.

The Department of Anesthesia's DSMB will review the study on an annual basis. Any adverse events will be reported and reviewed by the DSMB. Adverse events will be reported to MUSC's IRB per policy.

All data will be kept in a locked office, in a locked cabinet, and electronic data will be stored on a password protected MUSC server or redcap database. Only CITI certified, IRB approved study team members will have access to data.

14.0 Withdrawal of Subjects (if applicable)

- Circumstances under which subjects will be withdrawn from the research without their consent include severe allergy/intolerance to NAC.
- Subjects may withdraw from the study at any time. If patients voluntarily withdraw from the research study, they will receive our institutional standard of care for perioperative pain management.

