15.0 Risks to Subjects

- IV NAC can cause rate related anaphylactoid reactions in 0.2-18% of patients.^{22,23c} Most of the anaphylactoid reactions are mild (6%) or moderate (10%) with severe reactions (i.e., bronchospasm and hypotension) rare at 1% or less. Bronchospasm more commonly occurs in patients with pre-existing reactive airway diseases, like asthma. Bronchodilating agents are effective in treating these patients. To minimize this risk, patients with asthma, wheezing, or prescribed bronchodilators will be excluded from the study. Similarly, patients with a history of a prior anaphylactoid reactions to acetylcysteine will also be excluded.

If an anaphylactoid events occurs, patients will be treated as described by FDA guidelines.^b IV NAC will be stopped immediately and the patient treated with antihistamine medication (e.g., diphenhydramine) and IV fluids if required. Vasopressors are not typically necessary. NAC therapy may be restarted at a slower rate after resolution of any possible reaction. However, if an anaphylactoid reaction or

similar symptoms return upon reinitiating NAC treatment or increases in severity, IV NAC will be discontinued. Additionally, all possible medication reactions will be reported to the Anesthesia DSMB and MUSC IRB.

There is also a risk of loss of confidentiality.

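### Severe NAC intolerance ends participation in the research, not just the infusion, and no analysis population brings these patients back; the expected bias is small but avoidable by wording alone

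*Protocol*

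**What the plan says.** Protocol Section 14.0 sets out when a patient is taken out without their agreement: "Circumstances under which subjects will be withdrawn from the research without their consent include severe allergy/intolerance to NAC". What ends is participation in the research; the infusion is not mentioned.

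Section 6.0 sets the enrolment rule: "We will plan to consent 70 subjects to account for withdrawal but will complete the study once 50 or 60 subjects" have finished the protocol. The planning figure there is 20 per group, giving a 95% interval for the mean difference "with a width of ± 0.64 standard deviations from the mean".

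Section 15.0 gives the risk: "IV NAC can cause rate related anaphylactoid reactions in 0.2-18% of patients". It splits this into mild (6%), moderate (10%) and severe (1% or less, exemplified by bronchospasm and hypotension). For a reaction it speaks of stopping the infusion, possibly restarting it more slowly, and discontinuing NAC if symptoms recur or worsen. It does not say that the patient leaves the study.

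Section 10.0 places the single 60-minute infusion during surgery and sets time zero at the end of anaesthesia. It lists the electronic record as a data source alongside patients' self-reported pain scores. The SAP estimates the 12-hour difference from a linear mixed model with a random patient effect. Neither document defines an analysis population or says whether outcomes are collected after withdrawal.

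**The concern.** The reason for removal arises after randomisation and is tied by name to the active drug, so it will act mainly on the NAC side. The outcome clock starts after the infusion. A patient withdrawn for a reaction during the infusion therefore has no postoperative measurement, and the mixed model, which can use partial follow-up, has nothing to use. Because the trial runs to a number of completers, later patients make up the count.

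The comparison then tends towards NAC in those who tolerate it against all placebo patients, instead of the effect of being assigned NAC. Phase 1 is the more sensitive place, because each dose group has only five patients and these groups determine the dose carried forward. The phase 1 patients on placebo and the chosen dose also count towards the final 20 per group.

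The plan does not need this loss. The infusion is the only research procedure (Section 10.0), and opioid use can be read from the record whether or not the infusion was finished.

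**Working it through.** **Inputs.** Twenty per group, half-width 0.64 SD, five per dose group in phase 1 (Section 6.0). Severe reactions 1% or less, moderate 10%, all reactions up to 18% (Section 15.0). The documents give no opioid data for reactors, so the difference *d* between reactors and other patients in the same arm is an assumption: 0.5 to 2 SD, either sign.

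**1. The plan's own figure.** Half-width = t(0.975, 38) × √(2/20) = 0.640 SD. This reproduces the stated 0.64.

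**2. Expected removals from the chosen-dose arm.** Expected number = 20p; chance of at least one = 1 − (1 − p)^20. If a fraction p of the arm is dropped, the full-arm mean is m + pd and the completers' mean is m, so the arm mean shifts by pd.

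| Reading of the rule | p | Expected of 20 | Chance of at least one | Shift for d = 0.5 to 2 SD | Share of 0.64 SD |
|---|---|---|---|---|---|
| Severe only | 1% | 0.2 | 18% | 0.005 to 0.02 SD | 1% to 3% |
| Moderate plus severe (10% + 1%) | 11% | 2.2 | 90% | 0.055 to 0.22 SD | 9% to 34% |
| Upper limit, all reactions | 18% | 3.6 | 98% | 0.09 to 0.36 SD | 14% to 56% |

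The first row is the plain reading of Section 14.0. The other two show sensitivity to how intolerance is judged.

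**3. If one reactor is removed and the arm is later made up to 20.** The shift is d/21, or 0.024 to 0.095 SD.

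**4. Phase 1.** Fifteen of the first 20 patients receive NAC. At 1% the chance of any severe reactor among them is 1 − 0.99^15 = 14%. If one occurs and is not made up, a five-patient group shifts by d/5 = 0.10 to 0.40 SD. If the group is made up to five, the shift is d/6 = 0.08 to 0.33 SD.

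**5. Whole trial at 1%.** The 50-completer path has 15 + 15 = 30 NAC patients: 0.3 expected, 26% chance of at least one. The 60-completer path has 30 + 10 = 40: 0.4 expected, 33%.

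**6. Precision if reactors are kept.** With half-width t(0.975, n₁ + n₂ − 2) × √(1/n₁ + 1/n₂), keeping 1, 2 or 4 reactors in addition to 20 completers per arm gives 0.632, 0.624 or 0.611 SD. If enrolment is counted on all who started the infusion, 20 per group gives the planned 0.640. Losing 1, 2 or 4 without making them up gives 0.649, 0.659 or 0.682.

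**The case against.** The strongest reply is that *severe* governs the whole phrase, so only the 1% row applies. Not every reaction ends even the infusion, since Section 15.0 allows a restart, and Section 5.0 excludes active asthma, bronchodilator use and earlier reactions to acetylcysteine. On that reading there is an 82% chance that no one in the 20-patient arm is affected. This stands, and it sets the size of the point.

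A second reply is that Section 6.0 is a rule for stopping enrolment and that nothing written bars withdrawn patients from the analysis. This stands in part. The SAP is silent, but Section 14.0 is not: it takes the patient out of the research before time zero, and no other text brings the patient back.

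Three stronger readings are tempting and not supported:

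- *Reactors are replaced within their arm.* This is only inferred from the completer count. Phase 1 is counted by randomisation and enrolment, and no text gives a later patient the withdrawn patient's allocation.
- *Removals occur almost only on NAC.* This is likely, but the trial is blinded, and an event in a placebo patient could be taken for NAC intolerance.
- *The estimate is biased in a known direction.* Nothing in the documents says whether reactors would use more or less opioid.

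Finally, the consent pages are not available, so what they allow after withdrawal cannot be checked.

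**Conclusion.** The point holds as a small, avoidable source of bias. The plan removes patients after randomisation for a reason that arises mainly on NAC, before any outcome is recorded, and neither document corrects for it. At the protocol's severe rate, the expected shift in the 20-per-group comparison is 0.005 to 0.02 SD in either direction, at most about 3% of the planned half-width.

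A reader might infer that the randomised comparison is broken. The figures do not support that for a pilot planned on interval width. The effect becomes material only if *intolerance*, which is undefined, is applied to moderate reactions, or if a reactor falls in a five-patient phase 1 group. The results rest on the Section 15.0 rates applying to surgical patients and on the assumed *d*.

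**What to change.** - **Protocol Sections 14.0 and 15.0.** Reconcile them so that ending the infusion does not by itself end participation. This leaves unchanged when an infusion is stopped or restarted, which is for the sponsor to settle. State that opioid data continue to be taken from the medical record, over the planned 48 hours or to discharge, unless the patient withdraws consent.
- **SAP.** Define the primary analysis set as all randomised patients who started any infusion, analysed by assigned group, for both the phase 1 dose-response step and the phase 2 comparison. Report by arm the number whose infusion was stopped early.
- **Protocol Section 6.0.** Count enrolment on that set, so that only patients who never started the infusion are made up for.

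The cost is wording in two documents, plus a check that the consent form permits continued use of the record. Precision does not suffer, and the 70 planned consents leave 10 or 20 to spare over the 60 or 50 needed.
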